### 10.3.5 Investigator Reporting Responsibilities

The Investigator must immediately report all SAEs or SADEs (within 24 hours from time of learning of the event) to the sponsor using the supplied SAE/SADE reporting forms. Initial reports should be followed by detailed written reports. The investigator will determine whether the event was device related.

All SAE/SADEs are also captured and reported using the same terminology on the SAE/SADE Form in the Case Report Forms.

SAE/SADEs are emailed to:

Biointelect Pty Ltd Urgent Attention Safety Reporting [contact]
--

	QMS Template	Doc ID: RMI-ROBOTECHO-CIP-002 Ver No: V2.0
	Clinical Investigation Protocol	

The Investigator must also notify their respective HREC/s of any serious adverse outcomes immediately or as specified by the HREC guidelines.

### 10.3.6 Sponsor Reporting Responsibilities

The sponsor must report serious and unexpected adverse device events which are fatal or life threatening to the TGA using the Medical Device Incident Report Form within 7 calendar days of first knowledge. Follow-up reports are required within an 8 additional calendar days.

Other serious unanticipated device related events need to be reported to the TGA within 15 calendar days of first knowledge by the sponsor.

Non-serious and anticipated device related adverse events and other adverse events are recorded on the Case Report Form as part of Good Clinical Practice. Any safety issues emerging from an analysis of these events need to be notified to the TGA and relevant HRECs.

## 11 Statistics

The analysis and reporting will be conducted on all data from all participants at the time the study ends.

The statistical analysis plan will be finalised prior to database lock, and it will include a more technical and detailed description of the statistical analyses described in this section. This section is a summary of the planned statistical analyses of the most important endpoints.

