#### 11.1.1 Decision Criteria

The primary objectives of the study are to:

- assess the **safety** of the RUAT echo.
- assess the **“useability” (functionality)** of using the RUAT echo as intended to obtain echocardiogram images of clinically suitable quality for reporting by a cardiac sonographer.

The **safety** of the RUAT Echo will be considered acceptable if there are no device related adverse effects.

RUAT Echo will be considered a **useable** method of performing echocardiograms if:

- Each functional verification criteria 1 through 11 (inclusive) performed “YES” at least 80% of the time an echocardiogram was performed by RUAT Echo, that is, pass functional verification (see APPENDIX 1 - Functional Verification ).
- At least 80% of echocardiograms performed by RUAT Echo are considered of an adequate quality to provide a diagnostic assessment, that is, pass functional verification item #12 (see APPENDIX 1 - Functional Verification ).
- At least 80% of participants report they are satisfied with undergoing RUAT Echo examination based on an average of the 4 subscales of the 10-point Likert scales from strongly disagree to strongly agree (see APPENDIX 2 – Participant Survey).

	QMS Template	Doc ID: RMI-ROBOTECHO-CIP-002 Ver No: V2.0
	Clinical Investigation Protocol	

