#### 11.6 Sample Size Determination

Approximately 30 participants will be recruited. A single-group design will be used to obtain a two-sided 95% confidence interval for a single proportion of the RUAT Echo images that are deemed of sufficient quality. The Exact (Clopper-Pearson) formula will be used to calculate the confidence interval. The sample proportion is assumed to be 80%. With a sample size of 30, the width of the associated confidence interval is 30.9% around the 80% (that is, from 61.4% to 92.3%).

Confidence interval widths were computed using PASS 2023, version 23.0.2.

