### 15.3 Source Document and Data Verification

The study monitor will visit the investigational site periodically (approximately every 6 weeks or as deemed necessary) in accordance with the study monitoring plan. They shall:

- Meet with the investigator and any applicable site staff to discuss ongoing study compliance and data accuracy.
- Review all source documentation to verify CRF entries.
- Review the investigational site file and regulatory documentation.
- Ensure, where possible that CRF entries are corrected on site [in the first instance] should discrepancies be noted.
- Collect copies of documents and completed CRFs.

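### The SAP need only be final before database lock, although outcomes are unmasked and the score that makes a participant satisfied is not stated, so that cut-off could be set with results in view

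*Protocol*

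**What the plan says.** Section 11 (Statistics) says of timing only that "The statistical analysis plan will be finalised prior to database lock", and describes the SAP as a more technical account of the analyses summarised there. No earlier milestone, such as the first scan or first data review, is given.

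Section 11.1.1 (Decision Criteria) sets three useability conditions: items 1 to 11 of the functional checklist each pass in at least 80% of scans, item 12 passes in at least 80%, and at least 80% of participants are satisfied, "based on an average of the 4 subscales of the 10-point Likert scales". It gives no score at which a participant becomes satisfied. It describes the scales as running from strong disagreement to strong agreement. The four items in Appendix 2 are instead anchored on comfort, safety and visibility of the video, also without a cut-off.

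Section 11.3.2 gives a second useability rule, based on the 12 checklist items alone.

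On design, Section 11.6 says "A single-group design will be used to obtain a two-sided 95% confidence interval for a single proportion". On data flow, the monitor's tasks at site visits about every six weeks (Section 15.3) include: "Collect copies of documents and completed CRFs". Section 15.4 has data recorded on printed forms or sent electronically to the sponsor or its designee.

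**The concern.** Finalising a SAP before lock protects pre-specification when outcomes are masked until lock. Here they are not. The observing sonographer completes the checklist at the scan and supports or delivers the survey (Sections 4 and 10.2.1), and forms leave the site during the study. The protocol puts no limit on what the SAP's authors may have seen when they write it.

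That matters because one pass/fail criterion under a primary objective lacks its defining number. The criterion is judged on the observed share, so for a given set of scores the choice of cut-off can decide whether it is met. The sponsor manufactures the device, and Section 18 says the report may support regulatory applications. A satisfaction result would be hard to defend if nobody could show that the cut-off came before the scores.

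**Working it through.** **The plan's own figure.** Section 11.6 has n = 30 ("Approximately 30 participants will be recruited"), an assumed proportion ("The sample proportion is assumed to be 80" per cent) and the exact method ("The Exact (Clopper-Pearson) formula will be used to calculate the confidence interval"). With x = 0.80 × 30 = 24:

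- lower limit = Beta quantile 0.025 with parameters (24, 7) = 61.43%
- upper limit = Beta quantile 0.975 with parameters (25, 6) = 92.29%
- width = 30.85 percentage points

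This matches "the width of the associated confidence interval is 30.9% around the 80% (that is, from 61.4% to 92.3" per cent. The timing point does not affect it.

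**What is fixed and what is open.**

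| Element | Where | Status |
|---|---|---|
| 80% share for each useability criterion | 11.1.1, 11.3.2 | Fixed |
| Safety: no device-related adverse effects | 11.1.1 | Fixed |
| Analysis sets | 11.2 | Fixed |
| No imputation | 11.1.4 | Fixed |
| Exact 95% interval for image quality | 11.3.2.1, 11.6 | Fixed |
| Average score that counts as satisfied | 11.1.1, Appendix 2 | Not stated |
| Passing answer for checklist item 9 | 11.1.1, Appendix 1 | Ambiguous: a literal yes means the cables restricted the arm, but YES is the passing answer and the column asks whether the function performs as intended |
| Whether satisfaction is part of useability | 11.1.1 against 11.3.2 | Included in one, absent from the other |

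**When results could be seen.** Recruitment is put at two months (Sections 3 and 8) or about three (Section 8.1). Visits about every six weeks allow one or two collections of completed forms in that time, with the rest before lock. The only stated limit on data access (Section 20.1) covers one co-investigator with a declared conflict of interest.

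**How much a cut-off can matter.** The documents give no score distribution, so the following is assumed. Let a participant's four-item average be normal with mean m and standard deviation s. For cut-off c:

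- p = 1 − Φ((c − m)/s), treating the average as continuous
- p = 1 − Φ((c − 0.125 − m)/s), allowing for steps of 0.25 in a four-item average
- chance of meeting the criterion = P(X ≥ 24), X ~ Binomial(30, p)

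Each cell gives the continuous value, then the stepped value.

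| Assumed scores | c = 5.5 | c = 6 | c = 7 | c = 8 |
|---|---|---|---|---|
| m = 7, s = 1.5 | 81%, 89% | 34%, 46% | 0.1%, 0.2% | about 0% |
| m = 7.5, s = 1.5 | 98%, 99% | 81%, 89% | 4%, 8% | about 0% |
| m = 8, s = 1.5 | above 99% | 98%, 99% | 34%, 46% | 0.1%, 0.2% |
| m = 9, s = 1 | about 100% | about 100% | about 100% | 81%, 91% |

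For m = 7.5, s = 1.5 and c = 7, the continuous p is 1 − Φ(−0.333) = 0.631, giving P(X ≥ 24) = 0.037. The stepped p is 0.662, giving 0.075.

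If scores centre on 7 to 8, cut-offs between 5.5 and 8 take the criterion from likely or near-certain success to near-certain failure. If scores are very high, the choice matters much less.

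**The case against.** The strongest reply is that finalising a SAP before lock is common practice, that Section 11 confines the SAP to elaborating analyses already described, and that the real gap is one missing number. Much of this stands. Stating the cut-off in the protocol would remove most of the harm without moving the SAP milestone. It would not remove all of it, because the coding of item 9 and the conflict between Sections 11.1.1 and 11.3.2 would still be open.

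Three stronger readings are tempting, and the documents do not support them:

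- **The sponsor could set the overall result.** Satisfaction is one of three useability criteria in Section 11.1.1 and is absent from Section 11.3.2. A lenient cut-off cannot rescue a device that fails the checklist, and safety is judged separately.
- **The rules will be set with nearly all 30 results in hand.** This is possible but not shown. Form collection is by a contract research organisation's monitor, no formal interim analysis is planned (Section 11.5), and nothing says who writes the SAP or what that person sees. The wording creates an opportunity; it is not evidence of intent.
- **The co-investigator's financial interest reaches the data.** Section 20.1 bars that person from recording or accessing clinical study data during the trial. The bar does not extend to the rest of the sponsor, the contract research organisation or the SAP's author.

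It is also fair to say that this is a pilot summarised descriptively. Even so, Section 11.1.1 sets explicit pass/fail rules, and those need to precede the data.

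**Conclusion.** The concern holds in a limited form. As written, the protocol permits the satisfaction cut-off, the coding of item 9 and the choice of useability rule to be settled after unmasked results have been seen. Its other main decision rules are already fixed.

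The size cannot be derived from the documents. Under the assumed distributions, the cut-off alone can move the satisfaction criterion from 98-99% to 4-8% (mean 7.5, SD 1.5, cut-offs 5.5 and 7), or barely matter until cut-off 8, where 81-91% remains (mean 9, SD 1). These are chances of meeting one criterion, not of the study succeeding, and are illustrative only. That the study is open-label is inferred from the single group and the absence of any described blinding; the protocol does not use the term. This is a cheap improvement rather than a flaw that undermines the study.

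**What to change.** 1. In Section 11.1.1, state the average score at or above which a participant counts as satisfied, and align the description of the scale with the anchors in Appendix 2.
2. In Section 11, replace the lock milestone with wording such as: The statistical analysis plan, including every success cut-off and denominator, will be finalised and signed before the first RUAT scan. If scanning has begun, require it to be final before its authors see outcome data, and disclose the date.
3. State in the protocol or the early SAP which answer to checklist item 9 is a pass, and reconcile Sections 11.1.1 and 11.3.2 on whether satisfaction is part of the useability decision.
4. Date any later change and report it as post hoc.

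The cost is earlier drafting of a short SAP for a descriptive study of 30 people, plus a protocol amendment with ethics committee approval (Section 21.1). No participants or procedures are added, and the sample size and interval in Section 11.6 do not change.

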### 11.1 General Considerations

In general, data will be summarised descriptively. The number of participants tested and used in the final analysis will be summarised descriptively.

#### 11.1.1 Decision Criteria

The primary objectives of the study are to:

- assess the **safety** of the RUAT echo.
- assess the **“useability” (functionality)** of using the RUAT echo as intended to obtain echocardiogram images of clinically suitable quality for reporting by a cardiac sonographer.

The **safety** of the RUAT Echo will be considered acceptable if there are no device related adverse effects.

RUAT Echo will be considered a **useable** method of performing echocardiograms if:

- Each functional verification criteria 1 through 11 (inclusive) performed “YES” at least 80% of the time an echocardiogram was performed by RUAT Echo, that is, pass functional verification (see APPENDIX 1 - Functional Verification ).
- At least 80% of echocardiograms performed by RUAT Echo are considered of an adequate quality to provide a diagnostic assessment, that is, pass functional verification item #12 (see APPENDIX 1 - Functional Verification ).
- At least 80% of participants report they are satisfied with undergoing RUAT Echo examination based on an average of the 4 subscales of the 10-point Likert scales from strongly disagree to strongly agree (see APPENDIX 2 – Participant Survey).

	QMS Template	Doc ID: RMI-ROBOTECHO-CIP-002 Ver No: V2.0
	Clinical Investigation Protocol	

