### 8.1 Length of Study

Participants will be recruited until 30 participants have been recruited, estimated time is approximately 3 months.

Participants will undergo a single RUAT ECHO, which takes approximately 30-60 minutes.

Participants will undergo a single safety follow-up contact up to 72 hours ~~18-24 hours~~ after the RUAT ECHO is performed, either in person if inpatient or by telephone call/telehealth if outpatient/discharged patient.

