## 10 Study Procedures

Up to 30 participants will be required. Recruited participants will be RBWH Cardiology inpatients or outpatients who have already received a routine (manual) clinically reportable echocardiogram.

Study procedures and their timing are summarised in Figure 1 and the SoA (Section 4). Protocol waivers or exemptions are not allowed. Adherence to the study design requirements, including those specified in the SoA, is essential and required for study conduct.

All screening evaluations must be completed and reviewed to confirm that potential participants meet all eligibility criteria. The investigator will maintain a screening log to record details of all participants screened and to confirm eligibility or record reasons for screening failure, as applicable.

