### 10.3.2 Time Period and Frequency for Collecting AE, ADE, SAE and SADE Information

All AEs, ADEs, SAE and SADEs will be collected from the signing of the patient informed consent form (PICF) until 72 hours post RUAT Echo, i.e., end of the study.

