## 11.2 Analysis Sets

For the purposes of analysis, the following analysis sets are defined:

Participant Analysis Set	Description
Full analysis set (FAS)	All participants.
Safety analysis set (SAS)	All participants who are exposed to investigational medical device.

The full analysis set will be used to analyse endpoints related to the usability objectives and the safety analysis set will be used to analyse the endpoints and assessments related to safety.

All observed data will be used in the analysis.

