#### 11.3.2.1 Main Analytical Approach

The proportion of RUAT echocardiograms deemed to be of sufficient quality will be summarised descriptively along with a 95% confidence interval.

Participant experience will be summarised descriptively.

Adverse events and serious adverse events will be coded using the Medical Dictionary for Regulatory Affairs and will be summarised by system organ class and preferred term by echocardiogram type (conventional vs RUAT Echo). No statistical comparisons between adverse events or serious adverse events by scan type are planned.

Adverse device effects will be coded using the FDA Medical Device Report (MDR) adverse event codes and will be summarised by Level 1 Term and Level 3 Term by echocardiogram type (conventional vs RUAT Echo).

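### Section 11.1.1 calls safety acceptable after zero device-related effects in about 30 participants, without saying that 0/30 still allows a true rate of up to 11.6%

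*Protocol*

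**What the plan says.** Section 11.1.1 of the protocol states the safety criterion in one sentence: "The safety of the RUAT Echo will be considered acceptable if there are no device related adverse effects". It gives no tolerable event rate, confidence level or upper bound.

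Section 11.3.2.1 plans one confidence interval, and it is for image quality: "The proportion of RUAT echocardiograms deemed to be of sufficient quality will be summarised descriptively along with a 95% confidence interval". Adverse events and adverse device effects are tabulated by coded term, with no interval mentioned.

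Section 11.6 justifies the sample size on image quality alone: "A single-group design will be used to obtain a two-sided 95% confidence interval for a single proportion of the RUAT Echo images". The interval is to be exact (Clopper-Pearson). The target is stated as "Approximately 30 participants will be recruited" in Section 11.6 and as "Up to 30 participants will be required" in Section 10, while Section 8.1 says recruitment continues until 30 are enrolled.

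Section 8 describes the study as a pilot, and Section 18 says that the report may be used in support of regulatory approval applications.

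**The concern.** The plan turns the absence of observed events into a positive conclusion about safety. In a sample of this size, seeing none is weak evidence about how often an effect occurs, and nothing in the rule makes the reader aware of that. Image quality, the other quantity judged in Section 11.1.1, is at least reported with its uncertainty.

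The problem does not depend on poor ascertainment or misclassification. It remains if every event is found and classed correctly. If the plan is followed to the letter and no device-related effect is seen, the primary conclusion is that safety is acceptable, full stop. That statement could then enter a report with a possible regulatory use.

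**Working it through.** **Inputs**
- Rule: acceptable if the count of device-related adverse effects is zero (Section 11.1.1).
- Exposures: one scan per person, "Participants will undergo a single RUAT ECHO, which takes approximately 30-60 minutes" (Section 8.1).
- Denominator: "All participants who are exposed to investigational medical device" (safety analysis set, Section 11.2), so n is about 30.
- Observation window: from consent "until 72 hours post RUAT Echo, i.e., end of the study" (Section 10.3.2).
- Interval method: exact Clopper-Pearson, two-sided 95% (Section 11.6).
- Assumed: participants are independent. The true rates below are illustrations, because the protocol gives no expected or tolerable device-related rate.

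**Step 1. Reproduce the protocol's own figure.** For 24/30 (80%), the Clopper-Pearson limits from beta quantiles are 61.43% and 92.29%, a width of 30.85 points. Section 11.6 states 61.4% to 92.3% and a width of 30.9%, so its figure is correct and the same method can be carried over.

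**Step 2. Apply that method to zero events.** The two-sided 95% upper limit for 0/n is 1 − 0.025^(1/n).
- n = 30: 1 − 0.025^(1/30) = 0.1157, or 11.6%, roughly 1 in 9.
- n = 28: 12.3%. n = 25: 13.7%. A small shortfall changes little.
- A one-sided 95% bound at n = 30 would be 1 − 0.05^(1/30) = 9.5%. The two-sided limit is used here because it is the protocol's convention.

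**Step 3. How often the rule is passed.** With true per-participant rate p, the chance of zero events in 30 is (1 − p)^30.

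| Assumed true rate | Rule passed | Rule failed |
|---|---|---|
| 1% | 0.99^30 = 74.0% | 26.0% |
| 2% | 0.98^30 = 54.5% | 45.5% |
| 3% | 0.97^30 = 40.1% | 59.9% |
| 5% | 0.95^30 = 21.5% | 78.5% |
| 10% | 0.90^30 = 4.2% | 95.8% |

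The rate at which passing and failing are equally likely is 1 − 0.5^(1/30) = 2.28%. The rate caught with 80% probability is 1 − 0.2^(1/30) = 5.2%.

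**Step 4. What the rule can and cannot do.** It is a sensitive screen for effects in about one participant in ten or more. It says little about effects in one to a few per hundred.

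**The case against.** The strongest reply is that this is a declared pilot, summarised descriptively, with a rule that could hardly be stricter on observed counts. Section 10.3.1 lets an adverse device effect be mild, moderate or severe, so a single easily tolerated effect fails the criterion. At a true rate of 2% the rule rejects the device about 45% of the time. Read as a go/no-go check, it does not assert that rare events are excluded. This stands, and it is the reason to keep the criterion. It does not justify the word used for the outcome: strictness when an event is seen does not correct overstatement when none is.

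A second reply is that Section 11 is a summary, that a more detailed statistical analysis plan is to follow, and that an interval on an adverse-event proportion commonly belongs there. That is fair for the interval alone. The acceptance wording, however, is already fixed in the protocol, and an interval added elsewhere would sit beside an unchanged verdict.

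Third, the useability criteria are also observed proportions without a confidence bound. True, but they state a threshold (80%), and the image-quality proportion is reported with an interval. Safety has neither a tolerable rate nor an interval.

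A reader of the protocol might go further and infer that the rule lets a harmful device through more often than not. The documents do not support that. It is true only for true rates below about 2.3%, a range that has to be assumed. The events counted include mild ones, so the rate is not a rate of serious harm. Nor do the documents support a calculation at a much smaller sample such as 20: the wording that caps enrolment at 30 allows fewer, but Section 8.1 recruits until 30 and no section plans for 20.

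**Conclusion.** The point holds as a fault in how the primary safety conclusion is worded and reported. Zero device-related effects in 30 participants leaves a true rate of up to 11.6% compatible with the data at the two-sided 95% level. That limit rests only on n = 30, independent participants and the protocol's own interval method. The pass probabilities of 74%, 55% and 21% at true rates of 1%, 2% and 5% are illustrations under assumed rates.

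The rate in question is that of effects classed as device-related, of any severity, up to 72 hours. Section 10.3.4 lists bruising and discomfort among common procedure-related events, so what counts depends on that classification.

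It does not follow that the zero-event rule should be dropped or that the pilot is too small. Dropping it would leave a primary objective without a decision criterion, and a pilot need not exclude rates of a few percent, provided that it does not imply it has.

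**What to change.** 1. In Section 11.1.1, keep zero device-related adverse effects as the pilot go/no-go criterion, but change the conclusion attached to it. Suggested wording: *If no device-related adverse effect is observed, the result will be reported as no device-related safety signal observed in this pilot, together with the exact two-sided 95% Clopper-Pearson interval for the proportion of the safety analysis set with at least one such effect (upper limit 11.6% if 0/30).*
2. In Section 11.3.2.1, add that interval to the safety summary, to be reported whatever the count, using the number actually exposed as the denominator.

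The cost is two wording changes and one extra line in the safety table, with no additional participants or procedures. The downside for the sponsor is a less favourable statement: none observed, with rates of up to about 12% not excluded, in place of an unqualified finding of acceptability.

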**Table 2: Study objectives and endpoints**

Objectives	Endpoints
Primary	
To assess the safety of RUAT Echo	Adverse events Serious adverse events Adverse device effect Serious adverse device effects
To assess the useability (functionality) of using the RUAT echo as intended to obtain echocardiogram images of clinically suitable quality for reporting by a cardiac sonographer.	Verification of functional requirements Participant experience

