## 10.2.1 Evaluation

### 10.2.1.1 Functional verification of RUAT ECHO

The *Observing Sonographer* will complete a functional verification checklist (see APPENDIX 1 - Functional Verification ) to verify that the RUAT echo was performed as intended (as described in the Instruction Manual).

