### 11.3.2 Useability (functionality)

The RUAT Echo device will be deemed as being **sufficiently useable (functional)** (i.e., technically non-inferior) **if each of the 12 Functional Verification Criteria** (see APPENDIX 1 - Functional Verification ) result in "YES"  $\geq 80\%$  of the time.

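### The functional useability rule applies 80% to each checklist item separately, so it does not limit how many scans had a function fail; report the per-scan figure and word the verdict per function

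*Protocol*

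**What the plan says.** The second primary objective in Table 2 reads, in part, "To assess the useability (functionality) of using the RUAT echo as intended to obtain echocardiogram images of clinically suitable quality". Its endpoints are the verification of functional requirements and participant experience.

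Section 10.2.1.1 has the observing sonographer complete the Appendix 1 checklist "to verify that the RUAT echo was performed as intended". Each participant has one RUAT echo (8.1), so there is one checklist per scan.

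Section 11.1.1 sets three conditions for calling RUAT Echo useable:

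- Items 1 to 11: "Each functional verification criteria 1 through 11 (inclusive) performed “YES” at least 80% of the time an echocardiogram was performed by RUAT Echo".
- Item 12: "At least 80% of echocardiograms performed by RUAT Echo are considered of an adequate quality to provide a diagnostic assessment".
- Satisfaction: "At least 80% of participants report they are satisfied with undergoing RUAT Echo examination".

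Section 11.3.2 restates the functional rule: the device is sufficiently useable "if each of the 12 Functional Verification Criteria" reaches YES at least 80% of the time. The two sections agree that the benchmark is applied item by item. Neither defines a result for the whole scan across items. The only confidence interval described (11.3.2.1, 11.6) is for the proportion of scans with images of sufficient quality, which is item 12.

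**The concern.** The checklist answers a question about a scan: did this RUAT echo run as intended? The rule answers a question about a function: did this function work in at least 80% of scans? The answers differ whenever failures on different items fall in different scans.

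The conclusion in 11.1.1 is about RUAT Echo as a method of performing echocardiograms, and 11.3.2 glosses it as technical non-inferiority. Section 18 says a report may support regulatory applications. A reader of a positive verdict could take 80% to be the share of scans that ran without a functional failure. The rule does not establish that, and the true share could be far lower.

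**Working it through.** **Inputs.** "Approximately 30 participants will be recruited" (11.6), one scan each (8.1), so n = 30. Benchmark 80% per item (11.1.1, 11.3.2). Twelve items (Appendix 1). The protocol gives no item failure rates and no correlation between items, so these are assumptions below. Every item is taken as scored so that YES is favourable.

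**The plan's own figure.** The exact 95% interval for 24/30 has lower limit Beta(0.025; 24, 7) = 61.4% and upper limit Beta(0.975; 25, 6) = 92.3%, a width of 30.9 points. This reproduces 11.6.

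**Failures allowed.** An item passes with 0.8 × 30 = 24 YES, so 30 − 24 = 6 failures are allowed per item. That is 11 × 6 = 66 over items 1 to 11, and 12 × 6 = 72 over all items, against 30 scans.

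**Extremes at exactly 80% per item.**

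- Most clustered: all failures fall in the same 6 scans, and 24/30 = 80% of scans are fault-free.
- Most spread: 30/6 = 5 items, each failing in six different scans, put a failure in all 30. Those five items score 80%, the other seven (item 12 included) can score 100%, and the checklist criteria are met with 0% of scans fault-free.
- Three such items already affect 3 × 6 = 18 of 30 scans (60%).

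**Between the extremes.** If items fail independently with YES rate q, the fault-free share over 12 items is q^12. The chance of meeting the 12-item rule is P(X ≥ 24)^12, with X binomial(30, q).

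| q (assumed) | Fault-free scans, q^12 | P(one item passes) | P(12-item rule passes) |
|---|---|---|---|
| 80% | 6.9% | 0.607 | 0.25% |
| 90% | 28.2% | 0.974 | 73.1% |
| 95% | 54.0% | 0.9994 | 99.3% |

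**With within-scan correlation.** Independence is unfavourable to the device, so a Gaussian copula with equal latent correlation rho between items was used at q = 90%. Pass probabilities are simulated.

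| rho (assumed) | Fault-free scans, 12 items | P(12-item rule passes) |
|---|---|---|
| 0.3 | about 46% | about 76% |
| 0.6 | about 62% | about 81% |

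Clustering narrows the gap but does not close it at these values: the rule usually passes while roughly four to five scans in ten have some function fail.

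**The case against.** The strongest reply is that the protocol already has a scan-level success criterion. Item 12 requires reportable images in at least 80% of scans, and it drives the sample size and the interval. Section 10.2 says the RUAT echocardiograms are used only to judge whether the images can be reported. This stands. A reader might infer from the figures above that the device could be declared useable when most scans failed, but the documents do not support that: at n = 30, at least 24 scans must give reportable images. What is left open is how many scans had a function fail, not how many gave usable images.

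Second, the per-item rule fits the Table 2 endpoint, which speaks of functional requirements in the plural, and 11.1.1 and 11.3.2 agree with each other. That also stands; there is no internal contradiction.

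Third, one NO is not a failed examination. A poor telehealth screen (item 11) matters less when the performing sonographer is in the same room, and an all-items composite gives it the same weight as an arm that will not move. This is a good reason not to make the composite a pass/fail criterion. It is not a reason to leave it unreported.

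Fourth, items 3 to 6 describe successive steps, so their failures may well cluster. The 0% case is a worst case, and the 12-item conjunction is strict when every item is truly at 80% (0.25% under independence). Both are true, but the protocol does not say how failures cluster, and twelve separate rates cannot show it.

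Fifth, the SAP may tabulate failures per scan. It may, so the absence of that table from the protocol is not itself a fault. The decision rule and the wording of its conclusion, however, are fixed in the protocol.

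**Conclusion.** The point holds as a modest one: the functional verdict says more than the rule shows. Meeting 80% on each of items 1 to 11 is compatible with anything from 0% to 80% of scans being fault-free when the items sit at the benchmark. Item 12 and the satisfaction criterion do not narrow that range. At assumed item rates of 90% and latent correlation 0.3 to 0.6, about 46% to 62% of scans are fault-free and the 12-item rule passes about 76% to 81% of the time. These rates and correlations are illustrative; only the 0% to 80% range follows from the rule alone.

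A reader might go further and infer that the protocol owes a requirement that 80% of scans be free of any failure. The documents do not support that. The stated endpoint is function by function, image adequacy has its own scan-level criterion, and a composite threshold would be a new primary criterion: under independence it would need about 98.2% per item (0.8^(1/12)) for 80% of scans to be fault-free. Reasonable statisticians would differ on whether to want it.

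**What to change.** 1. In 11.3.2.1, add the number and proportion of scans with all of items 1 to 11 performing as intended, and the same for items 1 to 12. Give each the Clopper-Pearson 95% interval from 11.6 and show it next to the item rates.
2. In 11.1.1 and 11.3.2, word the functional verdict as what the rule shows: each function performed as intended in at least 80% of scans.
3. Do not add a per-scan 80% threshold as a decision criterion.
4. Before any count, fix the scoring of item 9 in Appendix 1. It asks whether the cables restricted the arm, so a literal YES is unfavourable, while the column is headed as performing as intended. The favourable answer should count as performing as intended.

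**Cost.** The data are already collected, so no extra participants, procedures or staff are needed: two table rows and a change of wording. The wording change is a protocol amendment and goes to the ethics committee under 21.1. The downside is presentational: the per-scan figure can never exceed the lowest item rate, so it may look less favourable than the item rates beside it.
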